Chronic pruritus of unknown origin (CPUO) is defined as itch lasting for more than 6 weeks without underlying systemic or neuropathic etiologies (Kim et al., 2019). CPUO presents on multiple segments of the body, and it is unresponsive to emollients. CPUO encompasses patients without a characteristic primary dermatologic eruption and negative systemic workup. Currently, there is a poor understanding of the etiology of CPUO, with eosinophilia and immune dysregulation suggested to play a role, but studies have been limited by small sample sizes (Kim et al., 2019; Patel et al., 2019). CPUO pathophysiology is hypothesized to involve several neuroimmune mediators, including histamine, IL-31, substance P, and TRPV1 (Miranda et al., 2018).

In this study, we would like to evaluate the safety and efficacy of abrocitinib, a Jak1 inhibitor, as a treatment for PN and CPUO. We hypothesize application of abrocitinib will improve these conditions of chronic itch, ultimately leading to improved overall quality of life via blockade of key cytokines known to be associated with conditions of itch including IL-31.

2. Objectives (include all primary and secondary objectives)

Approval Date: 3/16/2022
Principal Investigator: [name]
Application Number: IRB00262268

Primary Objective: To assess the efficacy of abrocitinib in reducing pruritus in patients with prurigo nodularis (PN) or chronic pruritus of unknown origin (CPUO) who are experiencing moderate to severe pruritus

Secondary Objectives:

- To evaluate the effect of abrocitinib in improving quality of life in patients with prurigo nodularis or chronic pruritus of unknown origin who are experiencing moderate to severe pruritus
- To evaluate the safety and tolerability of abrocitinib in subjects with prurigo nodularis or chronic pruritus of unknown origin who are experiencing moderate to severe pruritus

Exploratory Objectives:

- To evaluate the correlation between abrocitinib responsiveness and comorbidities in prurigo nodularis and chronic pruritus of unknown origin
- To evaluate the correlation between responsiveness to abrocitinib therapy with skin and blood biomarkers of prurigo nodularis and chronic pruritus of unknown origin

3. Background (briefly describe pre-clinical and clinical data, current experience with procedures, drug or device, and any other relevant information to justify the research)

Jak1, the target of abrocitinib, plays a critical role in signaling of many cytokines. Relevant for this application, Jak1 is involved in the signaling for IL-6 family cytokines including oncostatin M and IL-31, as well as for IL-4 signaling, all of which have been linked to chronic itch and prurigo nodularis (Campion et al., 2019; Ghoreschi et al., 2009; Zhang et al., 2008). Additionally, abrocitinib has been shown to inhibit IL-22 signaling in keratinocytes as well as various cytokine signaling pathways, including IFNa (Fetter et al., 2020; Silverberg et al., 2020).

As the etiology of PN and CPUO is unknown, and there are currently no FDA approved therapies, it is extremely difficult to treat patients with PN and CPUO. Prior investigations have suggested roles for aberrant keratinocyte signaling, neuronal dysregulation, and cutaneous inflammation (Hughes et al., 2020; Kowalski et al., 2019; Zhong et al., 2019). Targeted RT-qPCR and immunohistochemical staining have demonstrated dysregulation of select neurotrophic factors and cytokines, but these results were inconsistent (Fukushi et al., 2011; Matsumura et al., 2015; Park et al., 2011; Takada et al., 2013; Wong et al., 2020; Zhong et al., 2019). Similarly, previous studies have shown conflicting evidence of immune polarization (Fukushi et al., 2011; Park et al., 2011; Wong et al., 2020; Zhong et al., 2019).

In both CPUO and PN, there is evidence of involvement of IL-31 and Oncostatin-M (Kowalski et al., 2019; Salao et al., 2020); Sonkoly et al., 2006). IL-31 signals through binding the heterodimer receptor complex of Type-1 cytokine receptor IL-31RA and sub-unit OSMRb, which activates Jak1 for signal transduction (Zhang et al., 2008). PN has been studied more extensively than CPUO, and these studies have identified Th1/2 cytokine signatures as driving pSTAT6 and pSTAT3 nuclear localization in PN epidermis (Fukushi et al., 2011). As explained previously, there is conflicting evidence of immune polarization in PN. Notably, STAT6 and STAT3 activation and subsequent

Approval Date: 3/16/2022
Principal Investigator: [name]
Application Number: IRB00262268

nuclear localization is mediated by Jak1 activation, which itself is mediated by extracellular cytokine binding (Seif et al., 2017).

Abrocitinib is made by Pfizer, Inc. and is currently in Phase 3 trials for treatment of atopic dermatitis. At present, there is evidence that 200mg taken orally as a single daily dose is effective at reducing atopic dermatitis and itch associated from this condition. The incidence of adverse events with abrocitinib is well characterized and known adverse events will be monitored for during the course of this trial.

4. Study Procedures

- a. Study design, including the sequence and timing of study procedures (distinguish research procedures from those that are part of routine care).

- **Screening Visit**
- At the screening visit (**Visit 1**), eligibility for the study will be confirmed. This will entail:
 - Physical examination: Examination of major body organs.
 - Vital signs: Measurement of blood pressure, heart rate, respiratory rate, body temperature, height and weight.
 - Tuberculosis assessment: tuberculosis testing will be performed where indicated and as required by local health practice. This can be a skin test or a blood test.
 - Blood collection: The total amount of blood to be taken in this study for each participant is approximately 130mL (about 9 tablespoons). These samples will be used to test:
 - Complete Blood count, biochemistry (tests of kidney, thyroid and liver function).
 - IgE (immunoglobulin E) marker of inflammatory disorders
 - Hepatitis B and C test. The law requires us to report positive tests to the health department. This reporting will include information that identifies you (for example name, date of birth, home address, phone number, etc.) as required by Maryland law. The health department may use this information to contact you for further follow up and/or to help conduct health surveillance activities aimed at preventing or controlling diseases.
 - HIV screening test. You may be asked to sign a separate State of Maryland consent form for this HIV test. If the HIV test is positive it does not always mean you are infected with the HIV virus. It does mean you will need further testing and you will receive counseling about this. The law requires us to report positive tests to the health department. This reporting will include information that identifies you (for example name, date of birth, home address, phone number, etc.) as required by Maryland law. The health department may use this information to contact you for further follow up and/or to help conduct health surveillance activities aimed at preventing or controlling diseases.
 - Only for participants with known history of HIV: CD4+ T cell count and viral load will be evaluated at screening and

at the end of the study drug period. This will be approximately 10 mL (less than one tablespoon) blood in addition to total amount of blood.

- Pregnancy testing: only for women capable of having children: by blood test at the first study visit and urine sampling test every 4 weeks at site visit.
- **For Study Visits 2 through 7 (Week 0 – 16) the following procedures will be done according to the schedule above: Visits will be conducted within the specified week or within +/- 5 days of the intended week.**
 - Dispensing of Investigational Drug: All participants will receive abrocitinib beginning at visit 2. This will be taken as a daily oral dose of 200mg in tablet form. This therapy will continue for 12 weeks (through visit 6).
 - Electronic diary: Participants will be asked to complete a diary daily in the morning. This will include questionnaires to evaluate the severity of symptoms such as itch and pain and asking participants to rate their quality of sleep during the last night. The completion of the diary will take approximately 10 minutes. The study doctor or site staff will train participants on how to use the diary during Visit 1 and give you instructions on how to complete these assessments. This diary must be returned to the site at the end of study visit.
 - Questionnaires: Participants will need to complete up to 6 questionnaires on a tablet. This will provide insight into how their disease is affecting their quality of life and to provide information on symptoms and the impact of the disease on quality of life. Total duration of completion of these questionnaires will take approximately 30 minutes. Also, the study doctor will need to evaluate the severity of symptoms and complete up to 2 questionnaires at each visit. These questionnaires include:
 - PP-NRS
 - DLQI
 - PROMIS PIQ T Score
 - 5D Pruritis Score
 - SD-NRS
 - EQ-5D
 - HADS
 - PAS
 - PN-IGA
 - Physical examination: Examination of major body organs.
 - Vital sign: Measurement of blood pressure, heart rate, respiratory rate, body temperature, and weight.
 - Photographs: Digital photographs of the pruritic areas will be taken at each study visit. These photographs will avoid any identifying areas/marks including the face, tattoos or identifying birth marks.
 - Skin biopsy: A 4mm punch biopsy of the affected pruritic area will be taken at visit 2 and visit 6. This will involve injection of lidocaine and epinephrine followed by taking the biopsy. Participants will not feel pain, only pressure. A stitch will be placed and care instructions will be given. Participants will return for suture removal 7 to 10 days after the biopsy.

Approval Date: 3/16/2022
 Principal Investigator: [name]
 Application Number: IRB00262268

- Blood collection at all visits. The total amount of blood to be taken in this study for each participant is approximately 130mL (approximately 9 tablespoons). These samples will be used to test:
 - Hematology (blood count), biochemistry, Biomarker testing

Examination	Visit 1 Screening Week (-4)	Visit 2 (Week 0)	Visit 3 (Week 2)	Visit 4 (Week 4)	Visit 5 (Week 8)	Visit 6 (Week 12)	Visit 7 (Week 16)
Informed Consent	X						
I/E criteria – Full list above, but tests include: TSH, Hepatitis panel, HIV antibodies, CD4 count, CBC, CMP, lipid panel, PPD test, hCP test for pregnancy among WOCBP. Blood draw criteria is below.	X	X					
Demographics & Medical History	X						
Vital signs	X	X	X	X	X	X	X
Skin examination	X	X	X	X	X	X	X
PP-NRS		X	X	X	X	X	X
DLQI		X	X	X	X	X	X
PROMIS PIQ T-Score		X	X	X	X	X	X
5D Pruritus Score		X	X	X	X	X	X
SD-NRS		X	X	X	X	X	X
EQ-5D		X	X	X	X	X	X
HADS		X	X	X	X	X	X
PAS		X	X	X	X	X	X
PN-IGA		X	X	X	X	X	X
Photographs*		X	X	X	X	X	X
Dispense abrocitinib		X	X	X	X		
Adverse Event Monitoring		X	X	X	X	X	X
Itch Diary Review/compliance			X	X	X	X	X
Skin biopsy		X				X	
Plasma/PBMC isolation from blood draw		X				X	X
Labs from Blood Draw (CMP, CBC, Lipid panel, IgE)	X	X	X	X	X	X	
Patient who are HBcAB-positive and HBV DNA-negative at baseline require HBV DNA monitoring		X	X			X	

Approval Date: 3/16/2022
Principal Investigator: [name]
Application Number: IRB00262268

b. If your study involves data/biospecimens from participants enrolled under other research studies with a written consent or under a waiver of consent, please list the IRB application numbers for those studies. Please note: Certificate of Confidentiality (CoC) protections applied to the data in source studies funded by NIH or CDC will extend to this new study if the funding was active in 2016. If this situation applies, Section 36, question 6 in the application will need to be answered "Yes" and "Hopkins Faculty" should be selected in question 7. No other documents are required.

N/A

c. Study duration and number of study visits required of research participants.

Participants will be in this trial for up to 20 weeks including screening and follow-up.

d. Blinding, including justification for blinding or not blinding the trial, if applicable.

This study will not be blinded. All participants will receive study drug therefore blinding is not applicable.

e. Justification of why participants will not receive routine care or will have current therapy stopped.

Participants will need to stop current therapy in order to qualify for the study. In order to clearly elucidate the efficacy of abrocitinib against PN and CPUO, it is important for concurrent therapies to be halted. It is also important to note that the majority of therapies offered to these patients have poor efficacy in controlling PN and CPUO.

Participants will continue to receive other routine care.

f. Justification for inclusion of a placebo or non-treatment group.

There is no placebo group in this study. As this is an early phase, small study, we will not include a placebo group. If the data is suggestive of efficacy, a full blinded, and placebo-controlled study will be done.

g. Definition of treatment failure or participant removal criteria.

Approval Date: 3/16/2022
Principal Investigator: [name]
Application Number: IRB00262268

Discontinuation Criteria

Discontinuation from Study Treatment

Temporary Interruption of Investigational Product

In some circumstances, patients may need to temporarily interrupt treatment as a result of AEs or abnormal laboratory values that may have an unclear relationship to investigational product.

For the abnormal laboratory findings and clinical events (regardless of relatedness) listed in [Table 1](#), specific guidance is provided for temporarily interrupting treatment and when treatment may be restarted. Retest frequency and timing of follow-up laboratory tests to monitor the abnormal finding is at the discretion of the investigator. Investigational product that was temporarily interrupted because of an AE or abnormal laboratory value not specifically covered in [Table 1](#) may be restarted at the discretion of the investigator.

Laboratory Measure	Action	Monitoring Guidance
Lipid parameters	Patients should be managed according to international clinical guidelines for hyperlipidemia	12 weeks after initiation of treatment and thereafter according to international clinical guidelines for hyperlipidemia
Absolute Neutrophil Count (ANC)	Treatment should be interrupted if ANC < 2×10^9 cells/L and may be restarted once ANC return above this value	
Absolute Lymphocyte Count (ALC)	Treatment should be interrupted if ALC < 0.5×10^9 cells/L and may be restarted once ALC return above this value	
Hemoglobin (Hb)	Treatment should be interrupted if Hb < 11 g/dL and may be restarted once Hb return above this value	Before treatment initiation (see exclusion criteria too) and thereafter according to routine patient management
Hepatic transaminases	Treatment should be temporarily interrupted if drug-induced liver injury is suspected	

[Table 1](#) Criteria for Temporary Interruption of Investigational Product

Hold Investigational Product if the Following Laboratory Test Results or Clinical Events Occur:	Investigational Product May be Resumed When:
Symptomatic herpes zoster	All skin lesions have crusted and are resolving
Infection that, in the opinion of the investigator, merits the IP being interrupted.	Resolution of infection that, in the opinion of the investigator, merits the IP being restarted.

Abbreviations: ALT = alanine aminotransferase; AST = aspartate aminotransferase; IP = investigational product; ULN = upper limit of normal.

Approval Date: 3/16/2022
Principal Investigator: [name]
Application Number: IRB00262268

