1.1.2. Permanent Discontinuation from Investigational Product

Investigational product must be permanently discontinued if the patient or the patient's designee requests to discontinue investigational product.

Discontinuation of the investigational product for abnormal liver tests should be considered by the investigator when a patient meets 1 of the following conditions:

- ALT or AST $>2.5 \times$ ULN
- ALT or AST $>2 \times$ ULN with the appearance of fatigue, nausea, vomiting, right upper-quadrant pain or tenderness, fever, rash, and/or eosinophilia ($>5\%$)
- ALP $>3 \times$ ULN that is deemed to be of liver origin and drug-related
- ALP $>2.5 \times$ ULN with the appearance of fatigue, nausea, vomiting, right upper-quadrant pain or tenderness, fever, rash, and/or eosinophilia ($>5\%$)

Investigational product should be permanently discontinued if any of the following laboratory abnormalities are observed:

- White blood cell count $<1000 \text{ cells}/\mu\text{L}$ ($1.00 \times 10^3/\mu\text{L}$ or $1.00 \text{ billion}/\text{L}$)
- ANC $<1000 \text{ cells}/\mu\text{L}$ ($1.00 \times 10^3/\mu\text{L}$ or $1.00 \text{ billion}/\text{L}$)
- Lymphocyte count $<500 \text{ cells}/\mu\text{L}$ ($0.50 \times 10^3/\mu\text{L}$ or $0.50 \text{ billion}/\text{L}$)
- Hemoglobin $<10.0 \text{ g/dL}$; ($<100.0 \text{ g/L}$)
- Platelet count $<75,000/\text{mm}^3$; ($<75.0 \times 10^9/\text{L}$)
- Creatinine (serum) $>1.5 \times$ ULN
- Total bilirubin $>1.5 \times$ ULN
- Diastolic: recurrent or persistent (≥ 24 hours) of symptomatic increase from baseline in the same posture, by $>20 \text{ mmHg}$

Note: Temporary interruption rules must be followed where applicable. For laboratory values that meet permanent discontinuation thresholds, investigational product should be discontinued. However, if in the opinion of the investigator the laboratory abnormality is due to intercurrent illness such as cholelithiasis or another identified factor, laboratory tests may be repeated. Only when the laboratory value meets resumption thresholds following the resolution of the intercurrent illness or other identified factor may the investigator restart investigational product after consultation with the Pfizer-designated medical monitor. In addition, patients will be discontinued from investigational product in the following circumstances:

- Pregnancy
- Malignancy
- HBV DNA detected with a value above limit of quantitation
- Development of a VTE (DVT/PE) during the study

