- Have symptomatic herpes simplex at the time of randomization.
- Have had symptomatic herpes zoster infection within 12 weeks prior to randomization.

Approval Date: 3/16/2022
Principal Investigator: [name]
Application Number: IRB00262268

- Have a history of disseminated/complicated herpes zoster (for example, ophthalmic zoster or CNS involvement).
- Have a positive test for hepatitis B virus (HBV) defined as:
 - a. positive for hepatitis B surface antigen (HBsAg), or
 - b. positive for hepatitis B core antibody (HBcAb) and positive for hepatitis B virus deoxyribonucleic acid (HBV DNA)

Note: Patients who are HBcAb-positive and HBV DNA-negative may be enrolled in the study but will require additional HBV DNA monitoring during the study.
- Have hepatitis C virus (HCV) infection (hepatitis C antibody-positive and HCV ribonucleic acid [RNA]-positive).

Note: Patients who have documented anti-HCV treatment for a past HCV infection AND are HCV RNA-negative may be enrolled in the study.
- Have evidence of HIV infection and/or positive HIV antibodies
- Patients with uncontrolled HIV defined as reported CD4+ counts of ≤ 250
- Have had household contact with a person with active TB and did not receive appropriate and documented prophylaxis for TB.
- Have evidence of active TB or latent TB
 - a.) Have evidence of active TB, defined in this study as the following:
 - Positive purified protein derivative (PPD) test (≥ 5 mm induration between approximately 2 and 3 days after application, regardless of vaccination history), medical history, clinical features, and abnormal chest x-ray at screening.
 - QuantiFERON®-TB Gold test or T-SPOT®.TB test (as available and if compliant with local TB guidelines) may be used instead of the PPD test. Patients are excluded from the study if the test is not negative and there is clinical evidence of active TB.
- Have received any of the following medications:
 - a. Biologic treatments for immunologic disease such as etanercept, infliximab, certolizumab, adalimumab, golimumab, tocilizumab, abatacept, ustekinumab, ixekizumab, secukinumab, or anakinra within 8 weeks of screening.
 - b. Cyclophosphamide (or any other cytotoxic agent), belimumab, or anifrolumab (or another anti-IFN therapy) within 12 weeks of screening.
 - c. Rituximab, any other B cell depleting therapies, or intravenous immunoglobulin (IVIg) within 24 weeks of screening.
- Treatment with any other JAK inhibitors within the past 12 weeks

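### HBV DNA is not scheduled between Week 2 and Week 12 in HBcAb-positive participants, so only the Week 2 result can trigger the mandatory HBV DNA stop while treatment remains

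*Combined protocol and SAP*

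**What the plan says.** Four parts of the protocol bear on this point.

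- **Eligibility (Section 5, hepatitis B exclusion, note).** "Patients who are HBcAb-positive and HBV DNA-negative may be enrolled in the study but will require additional HBV DNA monitoring during the study". No interval is given, so the schedule table is where the condition is put into practice.
- **Schedule (Section 4a table).** The row beginning "Patient who are HBcAB-positive and HBV DNA-negative at baseline require HBV DNA monitoring" is marked at Visit 2 (Week 0), Visit 3 (Week 2) and Visit 6 (Week 12). It is blank at Visit 4 (Week 4), Visit 5 (Week 8) and Visit 7 (Week 16).
- **Dosing (Section 4a).** Daily abrocitinib starts at Visit 2 and runs for 12 weeks, through Visit 6. The table shows dispensing at Weeks 0, 2, 4 and 8 and none at Week 12.
- **Stopping rule (Section 4g, 1.1.2).** The text reads "patients will be discontinued from investigational product in the following circumstances", and the list that follows includes "HBV DNA detected with a value above limit of quantitation". The wording leaves the investigator no discretion.

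**The concern.** A stopping rule based on a laboratory result can act only when the test is done. The protocol identifies a subgroup that needs HBV DNA monitoring, enrols it, and makes a quantifiable result a compulsory reason to stop. It then schedules no such test for most of the dosing period. Between Week 2 and Week 12 the rule works only if someone orders an unscheduled test. Drug is dispensed again at Weeks 4 and 8 with no scheduled check of this criterion, although blood is taken at both visits.

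What is at stake is the safety of the HBcAb-positive participants: someone whose virus becomes quantifiable after Week 2 could stay on drug until Week 12. The primary efficacy analysis is not affected.

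**Working it through.** **Is the row read correctly?** The table was extracted from PDF, so column alignment was checked on two rows whose visits also appear in prose. Read the same way, the biopsy row gives Visits 2 and 6, as the Section 4a text says. The plasma row gives Weeks 0, 12 and 16, as Section 4i says. The HBV DNA row therefore does fall at Weeks 0, 2 and 12.

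**Inputs.** Counting from first dose as Day 0: Week 2 = Day 14, Week 4 = Day 28, Week 8 = Day 56, Week 12 = Day 84 (end of dosing). The visit window is ±5 days (Section 4a).

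**Current schedule**
- Interval between the two post-dose samples: 84 − 14 = 70 days, or 10 weeks.
- Share of the dosing period: 70 / 84 = 83%.
- Shortest interval within windows: (84 − 5) − (14 + 5) = 60 days.
- Longest interval within windows: (84 + 5) − (14 − 5) = 80 days.
- Post-dose samples with treatment still to stop: one (Week 2). The Week 0 sample is a baseline. The Week 12 sample coincides with the end of therapy.

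**With Weeks 4 and 8 added**
- Intervals after Week 2: 28 − 14 = 14, 56 − 28 = 28 and 84 − 56 = 28 days. The longest is 28 days, or at most 28 + 10 = 38 days (38 / 7 = 5.4 weeks) within windows.
- Post-dose samples that can still shorten treatment: three.

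| Sample | Dosing days left | Scheduled now |
|---|---|---|
| Week 2 | 84 − 14 = 70 | yes |
| Week 4 | 84 − 28 = 56 | no |
| Week 8 | 84 − 56 = 28 | no |

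Days left are counted from sampling. The time for a result to come back would reduce each figure.

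**What else is scheduled in the gap?** The metabolic panel is drawn at Weeks 4 and 8. Under 1.1.2, raised transaminases or alkaline phosphatase lead only to this: "Discontinuation of the investigational product for abnormal liver tests should be considered by the investigator". Total bilirubin above 1.5 × ULN does call for permanent discontinuation, but that is a separate trigger. Suspected drug-induced liver injury, or an infection judged serious enough, can interrupt dosing. After an abnormal finding, "Retest frequency and timing of follow-up laboratory tests to monitor the abnormal finding is at the discretion of the investigator". None of these provisions requires HBV DNA to be measured.

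**The case against.** The strongest reply is that nothing in the protocol is breached. Section 5 asks for monitoring without an interval, and the schedule supplies a baseline, an early on-drug and an end-of-treatment test. Every periodic test leaves gaps, and the documents contain no onset pattern, reactivation rate or monitoring standard that would make 28 days adequate and 70 days too long. The subgroup is also not unobserved: liver chemistry and adverse events are reviewed at Weeks 4 and 8, and the investigator may test or stop at any time. The Week 12 sample still has value, because it looks back over the gap and follow-up continues to Week 16. The subgroup may be very small or empty.

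Much of this stands. There is no contradiction between sections, the figures describe how often the test is done and not patient risk, and the number affected is unknown. It does not follow that the rule works during the gap. The rule is triggered by quantifiable virus whatever the liver enzymes show, and a compulsory stop should not rest for ten weeks on an optional test. The protocol also has its own comparator: pregnancy is in the same list of mandatory stops and is tested every 4 weeks (Section 4a). No reason is given for treating HBV DNA differently.

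**Conclusion.** The concern holds. For HBcAb-positive, HBV DNA-negative participants, 70 of the 84 dosing days pass without a scheduled HBV DNA test, and Week 2 is the only scheduled post-dose test that can bring the mandatory stop into effect while treatment remains. This is a weakness in the safety schedule that should be corrected. It does not invalidate the trial.

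The conclusion rests on the schedule as printed and on therapy ending at Visit 6. If Visit 6 fell a few days early some tablets might nominally remain, but the text ends treatment at that visit and none is dispensed there. No event rate or time of onset is assumed, so the benefit is stated as test timing only and not as harm avoided.

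**What to change.** Mark HBV DNA at Visit 4 (Week 4) and Visit 5 (Week 8) for HBcAb-positive, HBV DNA-negative participants, using the blood draws already planned there. This brings the longest nominal interval to 4 weeks, the same as for pregnancy testing.

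The cost is two extra assays per affected participant and a minor amendment to an IRB-approved protocol. No visit is added, and if no such patient enrols no assay is run.

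Two optional additions are separate from the stopping rule:
- A third assay at the Week 16 draw, as post-treatment safety follow-up.
- A sentence stating that HBcAb-positive patients have HBV DNA measured at screening, with the result known before drug is dispensed. The screening text lists a hepatitis B test without itemising it, so this is a clarification and not a correction.

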- Have any of the following specific abnormalities on screening laboratory tests from the central or local laboratory:
 - a.) ALT or AST $>2 \times$ upper limits of normal (ULN) ((Treatment should be temporarily interrupted if drug-induced liver injury is suspected) See below for discontinuations.
 - b.) alkaline phosphatase (ALP) $\geq 2 \times$ ULN
 - c.) total bilirubin $\geq 1.5 \times$ ULN
 - d.) hemoglobin $<10 \text{ g/dL}$ (100.0 g/L) (Treatment should be interrupted if Hb $< 8 \text{ g/dL}$ and may be restarted once Hb return above this value)
 - e. total white blood cell count $<3000 \text{ cells}/\mu\text{L}$ ($<3.00 \times 10^3/\mu\text{L}$ or $<3.00 \text{ billion}/\text{L}$)
 - f. neutropenia (absolute neutrophil count [ANC] $<2500 \text{ cells}/\mu\text{L}$) ($<2.50 \times 10^3/\mu\text{L}$ or $<2.50 \text{ billion}/\text{L}$) (Treatment should be interrupted if ANC $< 2 \times 10^9 \text{ cells}/\text{L}$ and may be restarted once ANC return above this value)
 - g. lymphopenia (lymphocyte count $<500 \text{ cells}/\mu\text{L}$) ($<0.50 \times 10^3/\mu\text{L}$ or $<0.50 \text{ billion}/\text{L}$) (Treatment should be interrupted if ALC $< 0.25 \times 10^9 \text{ cells}/\text{L}$ and may be restarted once ALC return above this value)
 - h. thrombocytopenia (platelets $<100,000 \text{ cells}/\mu\text{L}$) ($<100 \times 10^3/\mu\text{L}$ or $<100 \text{ billion}/\text{L}$)
 - i. eGFR $<40 \text{ mL}/\text{min}/1.73 \text{ m}^2$ (Bedside Schwartz formula 2009) or serum creatinine > 1.5 times the ULN

In the case of any of the aforementioned laboratory abnormalities, the tests may be repeated once during screening, and values resulting from repeat testing may be accepted for enrollment eligibility if they meet the eligibility criterion

Approval Date: 3/16/2022
Principal Investigator: [name]
Application Number: IRB00262268

6. Drugs/ Substances/ Devices

- a. The rationale for choosing the drug and dose or for choosing the device to be used.

Drugs:

Abrocitinib 200mg oral tablet – This drug is a study drug that was selected due to its targeting of the Jak1 pathway. 200mg is the dose that has been through Phase 3 trials for treatment of atopic dermatitis and there is significant data available regarding the safety and availability of the drug at this dose.

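### Hemoglobin entry and hold limits do not fit together, and the exclusion list carries interruption limits that can never operate

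*Combined protocol and SAP*

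**What the plan says.** Three parts of the protocol set hematology limits.

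- **Section 4g, temporary interruption (laboratory table).** For Hb: "Treatment should be interrupted if Hb < 11 g/dL and may be restarted once Hb return above this value". The ALC limit is 0.5 x 10^9/L and the neutrophil (ANC) limit is 2 x 10^9/L. The monitoring cell of the Hb row speaks of the time before treatment starts and points the reader to the exclusion criteria.
- **Section 1.1.2, permanent discontinuation.** Drug is stopped at Hb below 10.0 g/dL, lymphocytes below 500 cells/µL, or ANC below 1000 cells/µL. A Note adds that interruption rules are mandatory where they apply and that a value past a permanent limit leads to discontinuation. Restart is possible only after an identified cause has resolved, the value has reached resumption thresholds, and the medical monitor has been consulted. The Note does not list those thresholds.
- **Section 5, laboratory exclusions.** The list opens: "Have any of the following specific abnormalities on screening laboratory tests from the central or local laboratory". Item d excludes "hemoglobin $<10 \text{ g/dL}$ (100.0 g/L"), and then adds an on-treatment rule: "Treatment should be interrupted if Hb $< 8 \text{ g/dL}$ and may be restarted once Hb return above this value". Item g does the same for lymphocytes: "Treatment should be interrupted if ALC $< 0.25 \times 10^9 \text{ cells}/\text{L}$ and may be restarted once ALC return above this value". Items f and a carry similar parentheses for ANC ("Treatment should be interrupted if ANC $< 2 \times 10^9 \text{ cells}/\text{L}$ and may be restarted once ANC return above this value") and for transaminases ("Treatment should be temporarily interrupted if drug-induced liver injury is suspected").

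The schedule in section 4a checks eligibility at Visits 1 and 2, takes a complete blood count (CBC) at Visits 1 to 6, and dispenses drug at Visits 2 to 5.

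**The concern.** A list of screening exclusions is the wrong place for on-treatment dosing rules. Of the four printed there, two agree with section 4g (ANC and transaminases) and two do not (Hb 8 against 11; ALC 0.25 against 0.5). The two that disagree also lie below the level at which drug is permanently stopped.

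The second problem does not depend on which text governs. The Hb entry limit (10) is lower than the Hb hold limit in section 4g (11). A patient can therefore satisfy the eligibility criteria at an Hb that the same protocol treats as a reason to interrupt drug.

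At stake is consistent handling. Two patients with the same Hb could be managed differently, or an eligible patient could spend part of a 12-week treatment period on hold at an Hb no lower than the one at entry.

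**Working it through.** There is no plan figure to reproduce. The check applies the printed limits to each value in the order that the Note in section 1.1.2 sets: stop if the value is below the permanent limit; otherwise hold if it is below the interruption limit; otherwise no hold.

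**Inputs**

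| | Entry excludes (sec. 5) | Hold (sec. 4g) | Hold (sec. 5 parenthesis) | Permanent stop (sec. 1.1.2) |
|---|---|---|---|---|
| Hb, g/dL | <10 | <11 | <8 | <10.0 |
| ALC, 10^9/L | <0.5 | <0.5 | <0.25 | <0.5 |
| ANC, 10^9/L | <2.5 | <2 | <2 | <1.0 |

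Unit conversion: 500 cells/µL = 0.5 x 10^9/L.

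**Hemoglobin**

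| Hb (g/dL) | Sec. 1.1.2 | Sec. 4g | Sec. 5 parenthesis | Eligible? | Outcome |
|---|---|---|---|---|---|
| <8 | stop | hold | hold | no | stop |
| 8 to <10 | stop | hold | no hold | no | stop |
| 10.0 to <11 | silent | hold | no hold | yes | depends on which text governs |
| 11 and above | silent | no hold | no hold | yes | treat |

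The section 5 limit sits 10.0 - 8 = 2.0 g/dL below the stop, so its hold range is empty. The outcome differs in one band of width 11 - 10.0 = 1.0 g/dL, and all of that band is eligible.

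**Lymphocytes.** Below 0.5 the stop applies under either text. At 0.5 or above neither text holds. No band differs. The 0.25 limit is 0.5 - 0.25 = 0.25 below the stop and is inoperative.

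**Neutrophils, as a control.** Entry 2.5, hold 2, stop 1.0: the hold range is 1.0 to <2 under both texts and no eligible value is held. This is the order one expects (entry above hold above stop). For Hb the order is entry 10, hold 11, stop 10.

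**Timing when section 4g governs.** Take a patient with a stable Hb of 10.5. The value passes item d at Visits 1 and 2. The first CBC after dosing starts is at Visit 3 (Week 2); 10.5 < 11, so the hold applies then at the latest. The Hb row allows restart only above 11, which is 0.5 g/dL higher than the value at which the patient was admitted.

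**Do other provisions close the gap?** The repeat-test provision in section 5 ("values resulting from repeat testing may be accepted for enrollment eligibility if they meet the eligibility criterion") uses the same limit of 10. The general laboratory exclusion in section 5 rests on investigator judgement. The discretion over retest timing in section 4g leaves the restart level unchanged.

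**The case against.** A reader might infer that the protocol gives opposite orders at Hb 10.0 to <11: hold under section 4g, treat under section 5. That goes too far. Section 5 never says to treat in that band; it only sets a lower interruption limit. A site that holds below 11 complies with both, because every value below 8 is also below 11, and both restart clauses are permissive. Context also favors section 4g, which is the section on interruption, while the section 5 text is a parenthesis in a screening list. All of this stands. It does not settle the matter, because no sentence gives section 4g precedence and its own Hb row sends the reader to the list that prints 8. It also leaves the entry-below-hold mismatch untouched.

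A reader might also infer that an eligible patient is on hold from the first dose. That needs the Visit 2 CBC result before Visit 2 dispensing, and it needs interruption to cover someone not yet dosed. The documents establish neither; Week 2 is the supportable date.

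A further objection is that section 4g leaves restart to the investigator for laboratory values outside its Table 1, and the extracted layout leaves unclear whether the Hb row belongs to Table 1. The row nevertheless has its own restart level, and discretion over restart would not cancel the hold.

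Finally, unsafe dosing at Hb 8 to <10 or ALC 0.25 to <0.5 might be inferred from the section 5 limits. The Note in section 1.1.2 rules this out: drug is stopped at those values whichever interruption text is read.

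**Conclusion.** The point holds, in two parts. First, the Hb and ALC interruption limits in section 5 contradict section 4g and can never operate as holds. For ALC this is editorial only; for Hb it leaves the governing limit unstated in one eligible band, 10.0 to <11 g/dL. Second, with section 4g governing, an eligible patient whose Hb stays in that band meets the hold by Week 2 at the latest and may restart only above 11.

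This rests on the permanent stops taking precedence, as the Note says, and, for the Week 2 statement, on an unchanged Hb. The consequence is a possible dose hold or uneven handling between patients. The documents give no Hb distribution, so they support neither a count of affected patients nor an effect on the Week 12 results. It is worth correcting, at modest priority.

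**What to change.** 1. Delete all four on-treatment interruption parentheses (transaminases, Hb, ANC, ALC) from the section 5 laboratory list, and state that section 4g alone governs interruption.
2. Have the medical lead align the Hb entry and hold limits so that no eligible value is held. One option is to exclude Hb below 11 at entry, giving entry 11, hold <11, stop <10. The other is to keep entry at 10 and choose a hold limit consistent with it and with the stop. A fixed limit of 10 would leave no separate hold band, because the stop already covers every value below 10; if a hold band is wanted, the limit could be set relative to baseline.
3. State that the section 4g limits are the resumption thresholds in the section 1.1.2 Note for ANC, ALC and Hb only. Section 1.1.2 lists seven laboratory stops, so the other four (white cells, platelets, creatinine, bilirubin) have no section 4g value and would need their own.

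The cost is one amendment with text edits in sections 4g and 5, and no extra tests, since the CBC is already scheduled at Visits 1 to 6. The first option in step 2 loses patients with Hb 10.0 to <11; the documents do not show how many.
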